1. ABBREVIATIONS

ACOS	Asthma COPD overlap syndrome
ADR	Adverse Drug Reaction
AE	Adverse Event
CI	Confidence Interval
COTE	Copd cO-morbidity Test
ENR	Subjects enrolled
FEV ₁	Forced expiratory volume in 1 st second
FVC	Forced vital capacity
ICS	Inhaled corticosteroid
IgE	Immunoglobulin E
LABA	Long-acting beta2-agonist
mMRC	Modified Medical Research Council
TLF	Tables/Listings/Figures shells
SADR	Serious Adverse Drug Reaction
SABA	Short-acting beta2- agonists
SAMA	Short-acting muscarinic antagonist
SAP	Statistical Analysis Plan

Document: \\bcnfs02\general\Hdmgener\MEDICAL AFFAIRS 28.02.2017 actualizada\8. SRO ESTUDIOS\RESPIRATORIO\1237-0070 NIS OPTI\11 - Clinical Trial Report\SAP\SAP - V 1.0\SAP OPTI version1.0 29052019.docx

Author:

Version Number: 1.0

Version Date: [29MAY2019]

Template No.: RWI_TP_BIOS0013 Revision 1

Reference: RWI_WI_BIOS0015

Effective Date: 15Jun2018

Copyright © 2018 All rights reserved. The contents of this document are confidential and proprietary to Holdings Inc. and its subsidiaries. Unauthorized use, disclosure or reproduction is strictly prohibited.

2. INTRODUCTION

This statistical analysis plan (SAP) describes the rules and conventions to be used in the presentation and analysis of treatment patterns and patient profile. It describes the data to be summarized and analyzed, including specifics of the statistical analyses to be performed.

This statistical analysis plan (SAP) is based on protocol version 1.0, dated 19 September 2017 and case report forms (CRFs) version 1.0, dated 28 June 2018.

3. STUDY OBJECTIVES

This study has been designed in order to describe the COPD patient profile of patients treated with or without ICS in primary care, in Spain.

3.1 Primary Objective

The primary objective is to describe the patient profile for patients treated with ICS at the time of study visit.

3.2 Secondary Objectives

The secondary objectives are:

- To describe the patient profile for patients not treated with ICS at the time of study visit.
- To assess the proportion and the number (count) of patients with COPD treated with ICS at the time of study visit with or without moderate-to-severe exacerbations, both in the previous 1 year and previous 2 years before the study visit.
- To assess the proportion and the number (count) of patients with COPD not treated with ICS at the time of study visit with or without moderate-to-severe exacerbations, both in the previous 1 year and previous 2 years before the study visit.
- Use of rescue medication.

Document: \\bcnfs02\general\Hdmgener\MEDICAL AFFAIRS 28.02.2017 actualizada\8. SRO ESTUDIOS\RESPIRATORIO\1237-0070 NIS OPTI\11 - Clinical Trial Report\SAP\SAP - V 1.0\SAP OPTI version1.0 29052019.docx

Author:

Version Number: 1.0

Version Date: [29MAY2019]

Template No.: RWI_TP_BIOS0013 Revision 1

Reference: RWI_WI_BIOS0015

Effective Date: 15Jun2018

Copyright © 2018 All rights reserved. The contents of this document are confidential and proprietary to Holdings Inc. and its subsidiaries. Unauthorized use, disclosure or reproduction is strictly prohibited.

- Adherence to treatment recommendations according GesEPOC guidelines.
- To describe ICS-related adverse events.

4. STUDY DESIGN

4.1 General Description

This non-interventional, descriptive, cross-sectional cohort and multicentre study will be conducted with COPD patients attended at Spanish Primary Care offices.

The design of the study imposes an only visit to be performed that will coincide with one of those performed by the patients as part of routine follow-up of their disease, without interfering with usual clinical practice of the investigator.

A specific therapeutic strategy has already been assigned to each included patient, based on routine practice and without interference with the physician's prescription habits. The observational nature of the study is ensured as no diagnostic or therapeutic intervention outside of routine clinical practice will be applied.

4.2 Study size

Due to the descriptive design of the proposed non-interventional study, a formal sample size calculation has not been performed based on statistical power and protection for type I error.

In previously published studies in Spain (Miravittles, 2015), 66% of patients in usual clinical practice attending to primary care are non-exacerbators and of these, 61% are treated with ICS, therefore approximately 40% of all patients are currently treated with ICS without having exacerbations in the prior year.

Assuming a sample size of 900 patients and 40% of the patients are treated with ICS at the study visit and did not have a moderate or severe COPD exacerbation in the prior year, the 95% confidence interval for this proportion would be between 36.8% (lower limit) and 43.2% (upper limit). To

Document: \\bcnfs02\general\Hdmgener\MEDICAL AFFAIRS 28.02.2017 actualizada\8. SRO ESTUDIOS\RESPIRATORIO\1237-0070 NIS OPTI\11 - Clinical Trial Report\SAP\SAP - V 1.0\SAP OPTI version1.0 29052019.docx

Author:

Version Number: 1.0

Version Date: [29MAY2019]

Template No.: RWI_TP_BIOS0013 Revision 1

Reference: RWI_WI_BIOS0015

Effective Date: 15Jun2018

Copyright © 2018 All rights reserved. The contents of this document are confidential and proprietary to subsidiaries. Unauthorized use, disclosure or reproduction is strictly prohibited.

Holdings Inc. and its

account for a 10% drop-out rate (patients with inconsistent, incomplete or missing data), the sample size becomes 1,000 patients.

Table 1. Scenario for estimated proportions by 95% confidence intervals (95% CI)

	1	2	3	4	5	6	7	8
Expected proportion	0.4				0.5			
Lower and Upper limit of 95% CI	(0.37;0.43)	(0.368;0.432)	(0.365;0.435)	(0.363;0.437)	(0.47;0.53)	(0.468;0.532)	(0.465;0.535)	(0.463;0.537)
Precision of estimation	0.030	0.032	0.035	0.037	0.030	0.032	0.035	0.037
N (at final analysis)	1000	900	753	674	1042	938	784	702
Dropout 10%	1112	1000	838	749	1159	1043	872	780

4.3 Description of the treatment

[figure not shown]
Patients in this study will have been prescribed a treatment for their COPD. They could have been prescribed ICS or not. Prescription of the treatments will have been done under the sole responsibility of the healthcare professional and before the study initiation visit.

In addition, no intervention, either diagnostic or therapeutic, will be applied to patients other than that used for routine clinical practice.

4.4 Study flow/schedule

The design of the study imposes only one visit to be performed that will coincide with one of those performed by the patients as part of routine follow-up of their disease, without interfering with usual clinical practice of the investigator.

Figure 1. Study scheme for study periods

After signing the informed consent (if patient agreed to participate in the study) patients will be asked to answer the breathlessness scale (mMRC) and the CAT – COPD Assessment Test at the unique study visit. Other variables needed to answer study objectives will be obtained directly from patient medical records. The end of the study visit is the end of the study for each patient.

4.5 Schedule of Events

The schedule of events can be found in Section 6 of the protocol (Milestones).

4.6 Changes to Analysis from Protocol

No changes in analysis or definitions included in the final protocol have been considered.

5. PLANNED ANALYSES

5.1 Interim Analysis

No interim analysis has been planned.

5.2 Final Analysis

All final, planned analyses identified in this SAP will be performed by Real-World Evidence Solutions (RWES) Biostatistics following SOPs. Final CSR will be performed using Boehringer Ingelheim template.

6. ANALYSIS SETS

6.1 Subjects enrolled (ENR)

Subjects enrolled (ENR) set will contain all subjects who provide informed consent for this study and are included in main database.

6.2 Full Analysis Set (FAS)

The Full Analysis Set (FAS) will contain all subjects who provide informed consent for this study (ENR set) and fulfill all selection criteria. To be eligible to participate in the study, patients must meet the following selection criteria. The patient will be considered included when he/she agrees to participate in the study by signing the informed consent. This analysis set includes patients fulfilling these conditions:

- 1) Written informed consent prior to participation.
- 2) Female and male patient ≥ 40 years of age.
- 3) COPD diagnosis more than 2 years before the study visit.
- 4) Previously confirmed COPD diagnosis (post-bronchodilator FEV1/FVC ratio $<70\%$)
- 5) Clinical data available 2 years before the study visit.
- 6) Ability to complete CAT – COPD Assessment Test.

Patients will be excluded from participating in this study, and will be excluded from this analysis set, if the following criterion is met:

- 1) Current participation in any clinical trial involving a drug or device.

Document: \\bcnfs02\general\Hdmgener\MEDICAL AFFAIRS 28.02.2017 actualizada\8. SRO ESTUDIOS\RESPIRATORIO\1237-0070 NIS OPTI\11 - Clinical Trial Report\SAP\SAP - V 1.0\SAP OPTI version1.0 29052019.docx

Author:

Version Number: 1.0

Version Date: [29MAY2019]

Template No.: RWI_TP_BIOS0013 Revision 1

Reference: RWI_WI_BIOS0015

Effective Date: 15Jun2018

Copyright © 2018 All rights reserved. The contents of this document are confidential and proprietary to Holdings Inc. and its subsidiaries. Unauthorized use, disclosure or reproduction is strictly prohibited.

- 2) A moderate or severe exacerbation (requiring oral corticosteroid, antibiotics or hospitalisation) during the study visit or within 4 weeks before the study visit.

6.3 Patients treated with ICS Analysis Set (PICAS)

The patients treated with ICS Analysis Set (PICAS) includes all patient in FAS set treated with ICS during the study period.

6.4 Safety Analysis Set - ICS

The patients in the Safety Analysis Set includes all patient in ENR set treated at least with one dose of ICS during the study period. All safety variables related with ICS will be analyzed using this analysis set.

6.5 Safety Analysis Set - SPIOLTO®, STRIVERDI®, SPIRIVA® or ATROVENT®

The patients in the Safety Analysis Set includes all patient in ENR set treated at least with one dose of SPIOLTO®, STRIVERDI®, SPIRIVA® or ATROVENT® during the study period. All safety variables related to Boehringer Ingelheim COPD drugs will be analyzed using this analysis set.

Document: \\bcnfs02\general\Hdmgener\MEDICAL AFFAIRS 28.02.2017 actualizada\8. SRO ESTUDIOS\RESPIRATORIO\1237-0070 NIS OPT\11 - Clinical Trial Report\SAP\SAP - V 1.0\SAP OPTI version1.0 29052019.docx

Author:

Version Number: 1.0

Version Date: [29MAY2019]

Template No.: RWI_TP_BIOS0013 Revision 1

Reference: RWI_WI_BIOS0015

Effective Date: 15Jun2018

Copyright © 2018 All rights reserved. The contents of this document are confidential and proprietary to Holdings Inc. and its subsidiaries. Unauthorized use, disclosure or reproduction is strictly prohibited.

7. GENERAL CONSIDERATIONS

The design of the study imposes an only one visit to be performed that will coincide with one of those performed by the patients as part of routine follow-up of their disease, without interfering with usual clinical practice of the investigator.

Data will be obtained from patient medical records and during the study visit. Most of data will be available in the charts but as a routine clinical practice, some data could be missing. Data will be collected through an eCRF, which will include all the study variables.

The Investigator will enter the patient following the user guide during the study visit will fill in the CAT – COPD Assessment Test and mMRC data electronically into the eCRF system.

Boehringer Ingelheim reserves the right to discontinue the study overall or at a particular study site at any time for the following reasons:

1. Failure to meet expected enrolment goals overall or at a particular study site
2. Emergence of any efficacy/safety information that could significantly affect continuation of the study
3. Violation of the study protocol, or the contract by a study site or investigator, disturbing the appropriate conduct of the study

7.1 Reference Start/End Date

Reference start date is date of study visit, collected in the eCRF as mandatory variable. For this retrospective chart review study, index date is defined as date for data collection (patients attending to the participant site).

Document: \\bcnfs02\general\Hdmgener\MEDICAL AFFAIRS 28.02.2017 actualizada\8. SRO ESTUDIOS\RESPIRATORIO\1237-0070 NIS OPTI\11 - Clinical Trial Report\SAP\SAP - V 1.0\SAP OPTI version1.0 29052019.docx

Author:

Version Number: 1.0

Version Date: [29MAY2019]

Template No.: RWI_TP_BIOS0013 Revision 1

Reference: RWI_WI_BIOS0015

Effective Date: 15Jun2018

Copyright © 2018 All rights reserved. The contents of this document are confidential and proprietary to Holdings Inc. and its subsidiaries. Unauthorized use, disclosure or reproduction is strictly prohibited.

7.2 Common Calculations

7.2.1 Body Mass Index (BMI)

The formula to obtain Body Mass Index is the following: $\text{BMI (kg/ m}^2\text{)} = \text{weight (kg)/ height}^2 \text{ (m)}$ and BMI will be categorized into 5 categories according to the World Health Organization (WHO):

- Underweight: $\text{BMI} < 18.5 \text{ kg/m}^2$
- Normal weight: $18.5 \text{ kg m}^2 \leq \text{BMI} \leq 25 \text{ kg/m}^2$
- Overweight: $25 \text{ kg/m}^2 < \text{BMI} \leq 30 \text{ kg/m}^2$
- Obese: $30 \text{ kg/m}^2 < \text{BMI} \leq 35 \text{ kg/m}^2$
- Severely Obese: $\text{BMI} > 35 \text{ kg/m}^2$

7.2.2 Number of Pack-years

The number of **pack-years** is equal to the number of cigarettes smoked per day divided by 20 and multiplied by number of years smoked. The formula used for current smokers and ex-smokers will be:

Number of pack-years (for smokers) = (packs smoked per day) × (years smoking)

Number of pack-years (for Ex-Smokers) = (packs smoked per day) × (years smoking)

7.2.3 Time since COPD diagnosis

The number of years since diagnosis will be obtained as the difference between year of study visit and year of COPD diagnosis (+1). Years since diagnosis could be categorized according quartiles (or percentiles).

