9.2 SETTING

Approximately 1,000 patients with COPD are planned to be included in the study. To minimize selection bias at the patient level, the first 5 consecutive patients from each site who met all inclusion criteria and none of the exclusion criteria will be enrolled from approximately April 2018 and during one year.

It is necessary to ensure that study population is representative of the entire national territory. Therefore, patients will be recruited from primary care centers in different geographical areas according to the distribution of the overall population in this area. Site selection will be performed in order to secure representativeness of the COPD population.

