9.2.2 Study population

To be eligible to participate in the study, patients must meet the following selection criteria. The patient will be considered included when he/she agrees to participate in the study by signing the informed consent.

Patients will be included in the study if all of the following criteria are met:

- 1) Written informed consent prior to participation.
- 2) Female and male patient ≥ 40 years of age.

- 3) COPD diagnosis more than 2 years before the study visit.
- 4) Previously confirmed COPD diagnosis (post-bronchodilator FEV₁/FVC ratio <70%)
- 5) Clinical data available 2 years before the study visit.
- 6) Ability to complete CAT – COPD Assessment Test.

Patients will be excluded from participating in this study if the following criterion is met:

- 1) Current participation in any clinical trial involving a drug or device.
- 2) A moderate or severe exacerbation (requiring oral corticosteroid, antibiotics or hospitalisation) during the study visit or within 4 weeks before the study visit.

In addition, a log of all patients included into the study (i.e. having given informed consent) will be maintained in the study file (ISF) at the study site.

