9.3.3 Covariates

Table 9.3.3:1 Covariates related to patient profile

	Data from Medical Charts	Data Measured at Study Visit
Age, gender, ethnicity.	X	
Height & weight (BMI auto-calculated) *	X	
Smoking history.	X	
Pulmonary function test - Spirometry # *	X	
Bronchodilator test # * (FEV ₁ increase, absolute values).	X	
Episodes of wheezing in exacerbations.	X	
COPD diagnosis (year)	X	

History of asthma (yes/no) and year of diagnose	X	
History of atopy (yes/no).	X	
Blood Eosinophilia (number of eosinophils and %) *	X	
Immunoglobulin E (Ig E) *	X	
Current COPD treatment (including ICS: start and stop dates, dose, reason) §	X	
History and details of Exacerbations (last 2 years).	X	
History of antibiotics and oral corticosteroids for COPD	X	
Comorbidities (COTE index)	X	
Concomitant medication.	X	
COPD GesEPOC 2017 phenotypes	X	
GOLD 2017 spirometric classifications (1, 2, 3, 4).	Auto-calculated	
GOLD 2017 patient groups (A, B, C, D).	Auto-calculated	
BODEx (BMI / % FEV ₁ / mMRC / severe Exacerbations)	Auto-calculated	
Breathlessness based on mMRC score.		X
QoL: CAT - COPD Assessment Test		X

* Last measure available

available in medical charts <12 months

§ Not including possible changes or new prescriptions done at study visit

The covariates will also be included as independent variables for multivariable analysis: COPD phenotypes, GOLD group, BODEx index, mMRC score and CAT – COPD Assessment Test.

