7.2.4 Time since Asthma diagnosis

In asthmatic patients, the number of years since diagnosis will be obtained as the difference between year of study visit and year of Asthma diagnosis (+1).

Document: \\bcnfs02\general\Hdmgener\MEDICAL AFFAIRS 28.02.2017 actualizada\8. SRO ESTUDIOS\RESPIRATORIO\1237-0070 NIS OPTI\11 - Clinical Trial Report\SAP\SAP - V 1.0\SAP OPTI version1.0 29052019.docx

Author:

Version Number: 1.0

Version Date: [29MAY2019]

Template No.: RWI_TP_BIOS0013 Revision 1

Reference: RWI_WI_BIOS0015

Effective Date: 15Jun2018

Copyright © 2018 All rights reserved. The contents of this document are confidential and proprietary to Holdings Inc. and its subsidiaries. Unauthorized use, disclosure or reproduction is strictly prohibited.

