11. DEMOGRAPHIC AND OTHER BASELINE CHARACTERISTICS

Demographic data and other baseline characteristics will be presented for the FAS. General statistical testing will be carried out for demographic or other baseline characteristics.

The following demographic and other baseline characteristics will be reported for this study:

- Age in study visit
- Sex
- Ethnicity
- Weight (kg), Height (cm), Body mass index (BMI) (kg/m^2) and categories
- Tobacco use (no-smoker, ex-smoker, smoker, packs/year)
- Time since diagnosis (years) - calculated relative to date of visit

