COTE Index (cat)	Low risk: COTE index <4 points High risk: COTE index ≥ 4 points.			

Table 9. COPD characteristics according to current treatment on ICS.

		Non - ICS	ICS	Total
Time since COPD diagnosis (years)	Valid N Mean (SD) Median (Q1-Q3) Min-Max N missing			
Time since COPD diagnosis (cat)	0-2 years >2-5 years >5 years			
COPD GesEPOC 2017 phenotypes	non-exacerbator, mixed COPD - asthma syndrome (ACOS) exacerbator with emphysema exacerbator with chronic bronchitis			
GOLD 2019 spirometric classification	Gold 1 – Mild Gold 2 – Moderate Gold 3 – Severe Gold 4 – Very severe			
GOLD 2019 patient groups (A, B, C, D).	Patient A Patient B Patient C Patient D			
BODEx Index	Valid N Mean (SD) Median (Q1-Q3) Min-Max N missing			

Document: \\bcnfs02\general\Hdmgener\MEDICAL AFFAIRS 28.02.2017 actualizada\8. SRO ESTUDIOS\RESPIRATORIO\1237-0070 NIS OPTI\11 - Clinical Trial Report\SAP\SAP - V 1.0\SAP OPTI version1.0 29052019.docx

Author: Version Number: 1.0
Version Date: [29MAY2019]

Template No.: RWI_TP_BIOS0013 Revision 1 Reference: RWI_WI_BIOS0015

Effective Date: 15Jun2018

		Non - ICS	ICS	Total
BODEx Index (cat)	Class I Mild: BODEx 0-2 points Class II Moderate: BODEx 3-4 points Class III Serious: BODEx 5-6 points Class IV Very serious: BODEx 7-9 points			
CAT score	Valid N Mean (SD) Median (Q1-Q3) Min-Max N missing			
CAT score (cat)	CAT <10: Low impact of COPD. CAT ≥10: Medium / high impact of COPD Low impact: 0 ≤ CAT ≤ 10. Moderate impact: 11 ≤ CAT ≤ 20. High impact: 21 ≤ CAT ≤ 30. Very high impact: 31 ≤ CAT ≤ 40.			
mMRC score	Grade 0 Grade 1 Grade 2 Grade 3 Grade 4			

Table 10. Analytic results according to current treatment on ICS.

		Non - ICS	ICS	Total
Blood Eosinophilia (%)	Valid N Mean (SD) Median (Q1-Q3) Min-Max N missing			
Number of eosinophils (%)	<2% ≥ 2%			
Blood Eosinophilia (cel/μl)	Valid N Mean (SD) Median (Q1-Q3) Min-Max N missing			
Number of eosinophils (cel/μl)	<100 cel/μl 100-299 cel/μl ≥ 300 cel/μl			
Immunoglobulin E (UI/ml)	Valid N Mean (SD) Median (Q1-Q3) Min-Max			

Document: \\bcnfs02\general\Hdmgener\MEDICAL AFFAIRS 28.02.2017 actualizada\8. SRO ESTUDIOS\RESPIRATORIO\1237-0070 NIS OPTI\11 - Clinical Trial Report\SAP\SAP - V 1.0\SAP OPTI version1.0 29052019.docx

Author:

Version Number: 1.0

Version Date: [29MAY2019]

Template No.: RWI_TP_BIOS0013 Revision 1

Reference: RWI_WI_BIOS0015

Effective Date: 15Jun2018

		Non - ICS	ICS	Total
	N missing			
Inmunoglobulin E (UI/ml)	≤100 UI/ml >100 UI/ml			

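### The (+1) in the SAP's time since COPD and asthma diagnosis overstates mean disease duration by about one year

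*SAP*

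**What the plan says.** SAP 7.2.3 derives years since COPD diagnosis as the "difference between year of study visit and year of COPD diagnosis (+1"). SAP 7.2.4 uses the "difference between year of study visit and year of Asthma diagnosis (+1") for patients with asthma. Neither section gives a reason for the added 1.

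The covariate table in Protocol 9.3.3 shows that only years are recorded: "COPD diagnosis (year") for COPD and "History of asthma (yes/no) and year of diagnose" for asthma.

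The results go to three table shells:
- Table 8 gives mean, median, quartiles and range of time since asthma diagnosis.
- Table 9 gives the same for COPD, plus the categories "0-2 years >2-5 years >5 years".
- Table 25, the univariate logistic analysis of inadequate ICS use, repeats those COPD categories.

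Eligibility under Protocol 9.2.2 requires a "COPD diagnosis more than 2 years before the study visit".

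**The concern.** Adding 1 to a difference of calendar years counts both the first and the last year as whole years. That suits a count of calendar years touched, but the variable is labelled as time since diagnosis in years, which is elapsed time. The elapsed time from an unknown day in the diagnosis year to a day in the visit year is, on average, just the year difference.

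The primary objective is to describe the profile of ICS-treated patients, and SAP 16.2.3 lists time since COPD diagnosis among the profile variables. In a descriptive study the reported level is itself the result, so a systematic shift in it matters even when no comparison changes.

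**Working it through.** **Inputs from the documents.** The formulas are in SAP 7.2.3 and 7.2.4, and the year-only recording is in Protocol 9.3.3. On visit timing, Protocol 9.2 says patients "will be enrolled from approximately April 2018 and during one year". Eligibility (more than 2 years) is in Protocol 9.2.2, and the category cuts are in SAP Tables 9 and 25. The plan states no numerical duration, so there is no figure to reproduce.

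**Assumptions.** The documents give neither the month of diagnosis nor the distribution of true duration. I assumed several distributions and let diagnoses fall throughout the year.

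**Algebra.** Let Yv and Yd be the visit and diagnosis years, and uv and ud the fractions of those years elapsed at visit and at diagnosis (each from 0 to 1).
- True duration: T = (Yv − Yd) + (uv − ud)
- SAP value: S = (Yv − Yd) + 1
- Excess: S − T = 1 − (uv − ud)

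The excess lies between 0 and 2 years and averages 1 when uv and ud have the same mean. For the plain difference, the error is −(uv − ud), between −1 and +1 with mean 0.

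**Two patients.**
- Diagnosed mid-December 2015, seen mid-January 2019: T = 3.08, S = 2019 − 2015 + 1 = 5, excess 1.92.
- Diagnosed mid-January 2016, seen mid-December 2018: T = 2.92, S = 2018 − 2016 + 1 = 3, excess 0.08.

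**Means.** Simulation of 2 million patients per row, visits uniform over 12 months from April 2018:

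| Assumed true duration (years) | True mean | Plain difference | SAP formula |
|---|---|---|---|
| Uniform 2 to 12 | 7.0 | 7.0 | 8.0 |
| Uniform 2 to 15 | 8.5 | 8.5 | 9.5 |
| 2 + exponential, mean 3 | 5.0 | 5.0 | 6.0 |
| 2 + exponential, mean 6 | 8.0 | 8.0 | 9.0 |

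**Sensitivity to visit timing** (2 + exponential, mean 6). The mean excess is +0.98 for visits from July 2018 to April 2019, +0.63 if all fall in October to December, and +1.38 if all fall in January to March. The sign does not change.

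**Medians and quartiles.** Against the plain difference these shift by exactly 1. Against true duration the shift varies, because S is a whole number. With uniform 2 to 12, Q1 goes from 4.5 to 6 (+1.5), the median from 7 to 8 (+1.0) and Q3 from 9.5 to 10 (+0.5). With 2 + exponential mean 6, the median goes from 6.16 to 7 (+0.84).

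**The other reading.** If (+1) belongs to the diagnosis year, the value is Yv − (Yd + 1). Its error is −1 − (uv − ud), between −2 and 0 with mean −1.

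**Categories.** A diagnosis more than 2 years before the visit forces Yv − Yd ≥ 2, so S ≥ 3 and the 0-2 row is empty for every eligible patient. For 2 + exponential mean 6, the share above 5 years is 60.7% true, 66.0% with the SAP formula and 55.9% with the plain difference.

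**The case against.** The strongest objection is that deleting the 1 and changing nothing else makes the categories worse. Eligible patients with a year difference of 2 would then fall in the 0-2 row, which eligibility excludes: 5.0% of patients (uniform 2 to 12), 3.8% (uniform 2 to 15) or 7.9% (2 + exponential mean 6). Misclassification over the three categories rises from 5.0% to 10.0%, from 3.8% to 7.7% and from 5.4% to 12.7%. This stands, and it is why the categories must be restated in the same edit. Those patients all have a true duration between 2 and 3 years, so moving them to the lowest remaining category removes their error. That leaves 10.0 − 5.0 = 5.0%, 7.7 − 3.8 = 3.9% and 12.7 − 7.9 = 4.8%, about the level the SAP formula gives now.

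Three stronger readings are tempting but not supported:
- **A conflict with SAP section 11.** That section lists "Time since diagnosis (years) - calculated relative to date of visit". It names the reference point and gives no competing formula, and 11.1 sends the reader to 7.2 for derivations.
- **Every summary statistic wrong by the same year.** This is true only against the plain difference. Against true duration the excess varies by patient and by quantile.
- **Distortion of the multivariable model.** Time since diagnosis is in neither the covariate list of SAP 16.1.3.1 nor that of 8.3. It is only a categorical row in the univariate Table 25 shell. SAP 7.2.3 also allows quartile categories, which a constant shift leaves unchanged.

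**Conclusion.** The point holds at modest size. As written, the formula overstates mean time since COPD and asthma diagnosis by about 1 year, or by about 0.6 to 1.4 years if visits cluster in one quarter. On the other reading of (+1) it understates the mean by about as much, so the wording needs correcting either way. Medians and quartiles are off by roughly 0.5 to 1.5 years against true duration.

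The descriptive levels in Tables 8 and 9 and the duration categories in Tables 9 and 25 are affected. The shift from the plain difference is the same for every patient, so the ICS versus non-ICS difference, the SD and tests on the continuous variable do not change. The primary endpoint does not use this variable.

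The result rests on visits spread over the planned year and diagnoses spread within theirs. The bounds of 0 and 2 years per patient need neither assumption.

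**What to change.** 1. Delete (+1) in SAP 7.2.3 and 7.2.4 and summarise visit year minus diagnosis year.
2. In the same edit, restate the COPD duration categories in Tables 9 and 25 on the whole-year difference. Drop the 0-2 row and place a difference of 2 in the lowest remaining category, for example 2-5 and >5.
3. Add a footnote that only the year of diagnosis is recorded, so some patients near the 5-year cut are misplaced (about 4% to 5% in the three scenarios under the objection).

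The cost is a few words in the SAP, two table shells and a line of code, with no new data. The downside is small: with whole-year differences, the share above 5 years reads somewhat low (55.9% against 60.7% in the exponential mean 6 scenario), where the present formula reads high (66.0%).
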